2.3 Point-of-Care Platforms

2.3.1 LumiraDX SARS-CoV-2 antibody test

Assay summary: The LumiraDx SARS-CoV-2 Antibody Test is a single use fluorescence immunoassay device designed to detect the presence of SARS-CoV-2 total antibody in human serum, plasma (dipotassium EDTA), venous whole blood (dipotassium EDTA), and fingerstick whole blood. The test is run on a microfluidic test strip which is inserted into a device that will display the qualitative results within 11 minutes of specimen application. Table 2 displays the sensitivity as a function of the number of days since a positive reverse transcription polymerase chain reaction (RT-PCR) test: averaging over the time since the first known positive test, the sensitivity is 97%. Using 240 specimens known to be negative, all specimens were found to be negative, giving an estimated specificity of 100% with a 95% CI of 99%-100%⁸. There are two targets: the Spike RBD and the Spike 1 (S1) and pan Ig antibodies directed against these targets are detected. A qualitative result is displayed on the device and a semi-quantitative measure of the fluorescence can be accessed as research use only. The device is portable and can be moved on a cart between uses.

| Time from positive RT-PCR test to blood collection (days) | Number of samples | Number and percent positive | 95% CI |
|---|-------------------|-----------------------------|----------|
| 0-7 | 17 | 15 (88.2) | 64%-99% |
| 8-14 | 6 | 6 (100) | 54%-100% |
| 15 or more | 49 | 49 (100) | 93%-100% |
| Total | 72 | 70 (97.2) | 90%-100% |

Table 2: Sensitivity of the LumiraDX assay for various numbers of days from a positive test.**Figure 1:** A depiction of the operation of the LumiraDX testing platform. Note that for this protocol only the specimen identifier will be captured by the instrument, not personal identifiers.

Principle of the assay: The test works using microfluidics. Serum, plasma, venous whole blood, or fingerstick whole blood are applied to the sample application area of the test strip and inserted in the instrument. Each test strip contains 4 channels: 2 channels for the RBD, 1 channel for S1, and 1 channel for controls. Fluid moves the specimen up into the cartridge where it is mixed with reagents including magnetic particles coated with the RBD, S1, or control depending on the channel. Antibodies in the serum, plasma, or whole blood specific for RBD or S1 bind to the magnetic beads. A secondary pan-human Ig antibody conjugated to fluorescence then binds to the antibodies. The magnetic particles are captured in a magnetic field, and any unbound antibodies are removed using air. The fluorescent signal is then measured.

The analysis is based on the amount of fluorescence the instrument detects within the measurement area of the test strip. The qualitative results are displayed on the Instrument touchscreen in approximately 11 minutes from the addition of sample as “Positive +” or “Negative -”. The semi-quantitative measure of the fluorescence can be accessed as research use only.

2.3.2 RightSign COVID-19 IgG/IgM rapid test

Assay summary: The RightSign COVID-19 IgG/IgM Rapid Test Cassette is a lateral flow immunochromatographic assay for the detection of SARS-CoV-2 antibodies in venous whole blood, serum, or plasma. The test is run on a disposable lateral flow device (test cassette). The test targets IgG or IgM antibodies specific for the Spike RBD. The readout of the assay is qualitative: positive for IgG and/or IgM or negative within 10-20 minutes of specimen application. Tables 3 and 4 summarize the sensitivity as a function of the number of days since the first positive polymerase chain reaction (PCR) test. Averaging over the number of days since first known positive test the sensitivity of the IgM assay is 93%, while the sensitivity of the IgG assay is 94%. Specificity was estimated using 210 specimens known to be negative and the result was negative for IgM 206 times and negative for IgG 209 times. This gives an estimated specificity of 98% with a 95% CI of (95%, 99%) for IgM, and an estimated specificity of 100% with a 95% CI of (97%, 100%) for IgG⁹. For analyses that simply treat the RightSign assay as positive or negative, the RightSign test will be considered positive if the test is positive for IgM or IgG.

| Time from positive PCR test to blood collection (days) | Number of samples | Number and percent positive | 95% CI |
|--|-------------------|-----------------------------|---------|
| 0-7 | 9 | 6 (67) | 30%-93% |
| 8-14 | 83 | 77 (93) | 85%-97% |
| 15 or more | 158 | 150 (95) | 90%-98% |
| Total | 250 | 233 (93) | 89%-96% |

Table 3: Sensitivity of the RightSign IgM assay for various numbers of days from a positive test.

| Time from positive PCR test to blood collection (days) | Number of samples | Number and percent positive | 95% CI |
|--|-------------------|-----------------------------|---------|
| 0-7 | 9 | 6 (67) | 30%-93% |
| 8-14 | 83 | 76 (92) | 83%-97% |
| 15 or more | 158 | 152 (96) | 92%-99% |
| Total | 250 | 234 (94) | 90%-96% |

Table 4: Sensitivity of the RightSign IgG assay for various numbers of days from a positive test.

Principle of the assay: This test uses anti-human IgM antibody (test line IgM), anti-human IgG (test line IgG) and goat anti-mouse IgG (control line C) immobilized on a nitrocellulose strip. The conjugate pad contains recombinant SARS-CoV-2 antigen (based on the Spike protein RBD domain) conjugated with colloid gold. During testing, the specimen binds with SARS-CoV-2 antigen-conjugated gold colloid coated particles in the test cassette. When a specimen followed by assay buffer is added to the sample well, IgM and/or IgG antibodies if present, will bind to COVID-19 conjugates making an antigen-antibody complex. This complex migrates through the nitrocellulose membrane by capillary action. When the complex meets the line of the corresponding immobilized antibody (anti-human IgM &/or anti-human IgG), the complex is trapped forming a colored line which confirms a reactive test result. Absence of a colored line in the test region indicates a non-reactive test result. To serve as a procedural control, a colored

line should always appear in the control line region, indicating that the proper volume of specimen has been added and membrane wicking has occurred.

Figure 2: A depiction of the operation of the RightSign testing platform.

3 Methodology

3.1 Study Design

There are several related questions that this protocol is designed to answer, and these are reflected in 2 different components of the design. There will be a cross-sectional study designed to evaluate how the POC test works in practice and how the results are related to the GenScript assay measured on a plasma sample collected at the same time as the fingerstick blood samples for the two POC tests to be evaluated. This will involve recruiting and consenting individuals presenting to the clinical sites with a positive test for SARS-CoV-2. Consenting participants will have a fingerstick for each POC test conducted. If a test fails, 1 additional fingerstick may be conducted for each POC test (so, up to 4 fingersticks may occur). In addition, a 9mL blood specimen will be collected. Participants and care providers will not be informed of test outcomes. After the fingersticks, blood collection, and responses to a set of standardized questions from a CRF, the participant will have completed involvement with the study. The blood specimen will allow for both a comparison with the GenScript assay and the assessment of the impact of processing, freezing, and shipping on the POC test results. There will also be a nested case-control study to understand how POC tests carried out on stored plasma specimens from completed TICO trials are related to outcomes measured in the TICO protocol. Consent from TICO participants has already been obtained for the use of their stored specimens, so the case-control study will not involve additional consent or the recruitment and follow-up of patients.

For the field test, POC platforms will be distributed to 20-30 sites in the US and internationally for completion of the two POC tests on 15 participants at each site. In addition to conducting the POC test on site as per the instruments' instructions (using blood from a fingerstick), a blood specimen will be obtained for processing, freezing, and shipping to a central lab for central testing using the GenScript assay and repeat POC testing using plasma. If a POC test is indeterminate the test will be repeated 1 time and the outcome of the indeterminate test and the second test will be recorded. If the second test is also indeterminate that will be recorded but the test will not be conducted again on that participant. This procedure applies to POC testing at the sites and at the central laboratory.

A nested case-control study will also be conducted to allow for testing of the association between antibody levels at baseline, as assessed by the POC tests and safety and efficacy outcomes among participants randomized to the placebo group in the bamlanivimab, sotrovimab, and BRII-196/198 trials of TICO. The case definition is death or time to sustained recovery that exceeds 28 days. To maximize the difference between cases and controls, controls are defined as those with a time to sustained recovery of no more than 16 days. With these definitions there are 68 cases and 77 controls for a total sample size of 145. Among these participants, 104 experienced a sustained recovery and 20 died.

Conduct of this nested case-control study will require use of the POC assay on stored specimens. One cannot conduct such tests in a batched fashion which makes this analysis time consuming. This testing will be facilitated by procuring multiple POC platforms at a central location. The use of multiple platforms will allow for multiple tests to be conducted in parallel which is more efficient since each specimen must be run one at a time, and each takes 10-20 minutes.

3.2 Study Objectives

3.2.1 Field test

The overall objective of the field test is to determine if a POC test can be used to identify individuals who lack endogenous antibodies. The **primary objective** is to test for an association between the outcome of the locally obtained POC test and the centrally obtained result from the GenScript assay on a blood sample obtained at the same time as the sample for the POC test. There are also a number of secondary objectives that will investigate the feasibility of this approach, and others that will help interpret the outcome of the primary objective. These are as follows:

1. Determine the frequency with which the POC test fails to give an unambiguous result.
2. Determine the time required to obtain a POC result.
3. Determine the magnitude of the association between the locally obtained POC test result by the 20-30 sites and the same POC assay on the same specimens determined centrally after processing, freezing, storing, and shipping.
4. Determine the magnitude of the association between the POC test result and the GenScript assay on the same specimens both determined centrally.

Secondary objective 3 will provide information on the impact of processing (centrifugation for plasma), freezing, storing, and shipping on the test results using the same assay while secondary objective 4 will provide a head-to-head comparison of the assays using the same specimen subjected to the same handling procedures. Specimen handling and the specific assay used both likely contribute to differences we may observe between the local POC test and the results from the GenScript assay.

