DESIGN EPOC is designed to examine the feasibility of conducting point-of-care (POC) tests for SARS-CoV-2 antibodies and compare the reproducibility of these tests to tests run at a central laboratory on specimens obtained from the same study participants at the same time. This will involve recruiting 375 individuals at 20-30 US and international sites who have tested positive for SARS-CoV-2 and consenting them to up to 4 fingersticks, the collection of 9 mL of venous blood and responding to a set of standardized questions. All these activities will take place during a single study visit. The whole blood from the fingersticks will be used to test for SARS-CoV-2 antibodies using 2 POC tests, both of which have a CE mark, emergency use authorization (EUA) from the US Food and Drug Administration (FDA) and are Clinical Laboratory Improvement Amendments of 1988 (CLIA) waived. Participants and their providers will be instructed that the results of these tests are not to be used for patient management and the results of the tests will not be shared with participants or their providers. The 9 mL of blood will be processed locally and shipped to a central repository in the US where it will be labeled with a specimen code that can only be matched to the participant's other data using a participant identifier at the Statistical and Data Coordinating Center at the University of Minnesota (UMN). UMN will only have the specimen code and the participant identifier: the matching of the participant identifier to a participant can only be done at the sites.

In addition to this cross-sectional study (also referred to as the field test below), a nested case-control study utilizing specimens already collected from participants in the Therapeutics for Inpatients with COVID-19 (TICO) trial will be conducted. Participants in the TICO trial have already consented to the use of their specimens for future research on COVID-19. The POC tests will be conducted on these specimens and compared to results that have already been generated using an assay at a central laboratory called the GenScript cPass assay (referred to here as the GenScript assay).

The 2 POC assays that will be investigated under this protocol are the LumiraDx SARS-CoV-2 Antibody Test and the RightSign COVID-19 IgG/IgM Rapid Test. Both platforms will be used on all specimens. It is not the goal of this study to impact the indications for either test.

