3.5 Data and Blood Collection Plan

After providing written informed consent, a CRF will be completed for each participant and blood will be collected by up to 4 fingersticks and by a venous blood draw of 9 mL (in an EDTA collection tube for aliquoting plasma after centrifugation into 4 2 mL cryovials, each with about 1 mL of plasma). The blood from the fingersticks will be used to conduct the POC tests and the plasma cryovials will be stored locally in a -70°/-80° freezer until they can be shipped to the central biorepository. The CRF will capture the outcome of the POC tests, the length of time from the start of the assay to recording the test outcome, and selected data collected on the TICO Screening and Baseline and Randomization forms. This will include

1. Participation in other INSIGHT studies.
2. Demographics.
3. Date of onset of COVID-19 symptoms.
4. Severity of COVID-19.
5. Oxygen requirements.
6. History of chronic comorbidities.
7. SARS-CoV-2 vaccination information.
8. Targeted concomitant medications.
9. Height and weight.

Two fingerstick samples of blood will be obtained, one for each POC test. The plasma samples collected will be used for determination of antibody and antigen levels, and central laboratory determination of the two POC tests.

All study procedures will be performed by study personnel. Training materials and the consent document will clearly state that the results of the POC tests are not to be used for patient management and so should not be shared with the patient or care giver. All study procedures must be performed within 24 hours of completing the written informed consent.

Information will be collected from site staff about ease of use of each platform.

4 Data Analysis

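### Secondary objective 3 of the field test compares fingerstick whole blood tested on site with frozen venous plasma tested centrally, not the same specimens, so it cannot isolate the effect of handling

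*Combined protocol and SAP*

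**What the plan says.** Section 3.2.1 defines secondary objective 3 as the magnitude of the association between the locally obtained POC result and "the same POC assay on the same specimens determined centrally after processing, freezing, storing, and shipping". It then gives the purpose: "Secondary objective 3 will provide information on the impact of processing (centrifugation for plasma), freezing, storing, and shipping on the test results". Section 3.1 makes a similar and somewhat firmer statement, that the venous specimen allows "the assessment of the impact of processing, freezing, and shipping on the POC test results".

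The specimens themselves are described elsewhere:

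- Section 1, for the local test: "The whole blood from the fingersticks will be used to test for SARS-CoV-2 antibodies using 2 POC tests".
- Section 3.1, for the venous specimen sent to the central laboratory: "central testing using the GenScript assay and repeat POC testing using plasma".
- Section 3.5: "The blood from the fingersticks will be used to conduct the POC tests and the plasma cryovials will be stored locally". The plasma comes from a 9 mL venous draw into an EDTA tube, centrifuged and aliquoted.

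Section 3.2.1 closes by naming specimen handling and the choice of assay as likely contributors to any difference between the local POC result and GenScript.

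**The concern.** Objective 3 describes a before-and-after comparison on one specimen: test it, process and ship it, test it again. On that description a local–central difference would be a handling effect. The procedures describe something else: two specimens, taken in different ways from the same participant and tested in different places.

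This matters for interpretation. Section 3.2.1 says some of the secondary objectives are there to help interpret the primary comparison. The outcome evidence in the nested case-control study comes from stored plasma (sections 3.1 and 4.4), whereas bedside use would rest on fingerstick blood. The local–central contrast in the field test is what connects the two. If a difference is credited to freezing and shipping, the bedside result looks sound and the stored-plasma result looks degraded. If it came from the fingerstick specimen or from reading the test on the ward, the reading would be reversed.

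**Working it through.** **Step 1. Set the two arms of the contrast side by side.**

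| Feature | Local POC test | Central POC test | Named in the stated interpretation of objective 3? |
|---|---|---|---|
| Blood source | Fingerstick (1, 3.1, 3.5) | Separate venous EDTA draw (3.5) | No |
| Matrix | Whole blood (1) | Plasma (3.1, 3.5) | In part, as centrifugation within processing (3.2.1) |
| Testing setting | Study personnel, on platforms distributed to 20–30 sites (3.1, 3.5) | Central laboratory (3.1, 3.5) | No |
| Freezing, storage, shipping | None | Yes (3.1, 3.5) | Yes |

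That operators and instruments differ between the two settings is inferred from where the tests are run; the documents do not say so outright.

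**Step 2. Does any part of the design isolate handling?** That would need the same matrix from the same draw to be POC-tested both fresh and after storage. The sites POC-test only fingerstick blood; no fresh plasma or fresh venous blood is POC-tested. All four features in the table change together in every participant.

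**Step 3. Can the models separate them?**

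- Section 4.2 fits a local/central term and site effects, and looks at whether the local–central difference varies by site. Such variation could hint at site operators or instruments, but processing and local freezing also vary by site. An effect common to all sites stays inside the local/central term.
- The pooled model in section 4.4 has terms for assay, local versus central, and protocol or sub-study. A local result is always fingerstick whole blood and a central one always plasma, so the local/central term again carries all the components.

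**Step 4. Check the plan's power figure and what it refers to.** Inputs from section 3.3.1 and Table 5: N = 375, discordance probabilities 0.03 and 0.078, odds ratio 2.6, significance level 0.05 (taken as two-sided).

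- Expected discordant pairs: m = 375 × (0.03 + 0.078) = 40.5.
- Conditional probability: P = 2.6 / 3.6 = 0.722.
- Power = Φ[(√m × (P − 0.5) − 1.96/2) / √(P(1 − P))] = Φ[(6.364 × 0.2222 − 0.98) / 0.448] = Φ(0.97) = 0.834, against 0.83 in Table 5.

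The figure reproduces, as do the other 20 cells of Table 5 to rounding, and nothing here changes it. It is power for the net difference, 0.078 − 0.03 = 0.048. On a simple additive view:

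net difference = source + matrix + setting + handling.

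The study yields one such estimate per POC test, which cannot be divided among four terms. McNemar's test addresses only the sum, so effects of opposite sign could also offset one another.

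**The case against.** Several arguments on the other side are sound and limit the point.

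- **The wording is soft.** Section 3.2.1 promises information on a bundle of steps. A reader might infer that the plan claims to measure freezing or shipping on its own; it does not say that.
- **Matrix is not ignored.** A reader might infer that the change from whole blood to plasma is overlooked. The reference to centrifugation names that step as part of processing. What goes unmentioned is fingerstick versus venous source and the testing setting.
- **The list of contributors is not exclusive.** Section 3.2.1 says handling and assay probably both contribute to differences from GenScript. It does not say nothing else does.
- **Reader effects are mainly a RightSign matter.** The LumiraDx instrument displays its own positive or negative result (section 2.3.1).
- **The site analysis has some bearing.** It can show whether the local–central difference varies across sites, though it cannot recover an effect shared by all of them.
- **The estimate itself is well defined.** Agreement between bedside and central testing is useful in its own right, and no decision rule in the documents depends on crediting a difference to handling.

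What survives is narrower. The specimens are not the same, two components of the contrast are unacknowledged, and neither design nor analysis can separate them from handling. The accurate descriptions in sections 1, 3.1 and 3.5 make the intent recoverable, but they contradict objective 3 and do not cure it.

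**Conclusion.** Wrong as written, minor severity. Objective 3 misdescribes the specimens, and sections 3.1 and 3.2.1 attach to the contrast an interpretation that the design supports only in part. What it estimates is the combined effect of specimen source and matrix, testing setting and handling.

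No size can be given. A reader might take the 4.8-point difference in the powered scenario as the amount misattributed. The documents do not support that: it is an illustrative planning value, and section 3.3.1 says no data exist for this comparison. Nor do they support the inference that the contrast is worthless or that the field test's main result is compromised. The primary objective (local POC versus GenScript) does not depend on the attribution. Secondary objective 4 is unaffected, because both of its tests are run centrally on the same stored plasma. No power figure changes.

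The conclusion assumes that the procedures in sections 1, 3.1 and 3.5 are carried out as described, and that operators and instruments differ between sites and the central laboratory.

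**What to change.** 1. In section 3.2.1, objective 3, replace the statement that the specimens are the same with: *specimens collected from the same participant at the same time*. Leave objective 4 as it is.
2. In sections 3.1 and 3.2.1, describe the local–central contrast as the combined effect of specimen source and matrix, testing setting (operator and instrument) and handling.
3. In the closing sentence of section 3.2.1, add specimen source and testing setting to the likely contributors to differences between the local POC result and GenScript.
4. State that no conclusion about freezing, storage or shipping alone will be drawn from this contrast.

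The cost is a narrower claim for objective 3. No new procedure, specimen, analysis or participant burden is involved, and the sample size stands. Isolating handling would require testing one matrix both fresh and after storage; that would be an addition to the study and is not needed to correct the text.
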